11.5.3 Assessments at the end of trial visit

At the end of the trial a health economic evaluation will be performed.

# 11.6 Schedule of Assessments

#### MAST-PROPHYLAXIS

Assessment	Screening/ baseline	Treatment phase end	Follow up			Follow up visits	End of Study
Visit	1	2	3	4	5	6	7
	Day 1	Day 7	Day 14	6 mths	12 mths	18 mths	24 mths
Eligibility assessments	х						
Informed consent	х						
Urine pregnancy test (if applicable)	х						
Randomisation	х						
ECG (if indicated by local policy)	х						
CRF Part 1	Х						
IMP administration	Х	Х					
AESI assessments and CRF completion	х	х					
Concomitant medications	х	Х					
Occurrence of seizures		Х	Х	х	х	х	х
GOS questionnaire				х	Х	х	х
NSI questionnaire				х	х	х	Х
EQ-5D-5L			х	х	х	х	х
questionnaire							
Liverpool Adverse				x	х	х	х
Events Profile							
questionnaire Economic evaluation							x

Assessment	Screening/ baseline		Treatment phase			Follow up visits	End of Study
Visit	1	2	3	4	5	6	7
	Day- 1	discharge	3 mths	6 mths	12 mths	18 mths	24 mths
Eligibility assessments	Х						
Informed consent	х						
Randomisation	х						
CRF stage 1		х					
Treatment duration<3mths	Х	х	х				
Treatment duration>6mths	х	х	х	х	x	x	x
AESI assessment	х	х		х			
Concomitant medications	х	х					
Occurrence of seizures	Х	Х		х	х	х	х
GOS questionnaire				х	х	х	х
NSI questionnaire				х	х	х	х
EQ-5D-5L questionnaire		х		х	х	х	х
Liverpool Adverse Events				х	х	х	х
Profile questionnaire							
Compliance check				х			
Economic evaluation							х

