#### 8.6.2 Secondary outcome measures (both trials)

- Occurrence and time to PTS within 24 months post-TBI (MAST-PROPHYLAXIS ONLY)
- Extended Glasgow Outcome Scale, Neurobehavioral Symptom Inventory, quality of life (EQ-5D-5L), and Liverpool Adverse Events Profile at 6, 12, 18 and 24 months.
- Economic evaluation
- Frequency of PTS
- Mortality at 6, 12, 18 and 24 months.
- Adverse events of special interest during treatment.

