## 10.1.1.4 . Maximum duration of treatment of a participant

MAST-PROPHYLAXIS: Participants will receive a course of 7 days of either phenytoin or levetiracetam or no drug.

MAST-DURATION: Participants will receive a maximum of up to 3 months or a minimum of 6 months as determined by the randomisation. The maximum possible duration of treatment during the trial is 24 months dependent on clinical need

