## 11.5 Trial assessments

## 11.5.1 Timing of assessments

Patients will be monitored as per routine clinical practice in the Neurosurgical Unit until discharge and thereafter at 6 months, 12 months, 18 months and 24 months (+/- 8 weeks at each time point) in both studies to score clinical outcome. Patients in the MAST-PROPHYLAXIS study will also be followed up at 14 days. Patients from the MAST-PROPHYLAXIS study may also be followed up at 60 months, subject to additional funding (+/- 8 weeks).

11.5.2 Assessments at time point

- Adverse events of special interest review during treatment.
- Assessment for seizures during hospital admission, at discharge at day 14 (by telephone if patient is already discharged) (PROPHYLAXIS only)
- EQ-5D-5L questionnaire at discharge

Follow up postal questionnaire/email/telephone call at 6 months (+/- 8 weeks), 12 months (+/- 8 weeks), 18 months (+/- 8 weeks), 24 months (+/- 8 weeks) post randomisation
 To document:

Occurrence of seizures

- GOSE questionnaire
- NSI questionnaire
- EQ-5D-5L questionnaire
- Liverpool Adverse Events Profile questionnaire

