#### MAST-DURATION

If clinical indicated

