#### MAST DURATION

A course of phenytoin or levetiracetam (up to 3 months) for patients with PTS in the acute phase. Hence, we are starting from the premise that the shorter AED duration is 'standard' practice. The longer AED duration course will potentially decrease the PTS rate. Therefore, the proposed study will be a superiority trial. In view of the potential for increase in side effects with a longer course, we will aim for a relatively large treatment effect of 13% (NNT 7.7), as this is felt necessary in order to lead to a change in clinical practice in the 'real -world'.

Recruiting 428 patients overall will provide 188 observations per arm. Assuming seizure rates of 12% and 25% in the intervention and control arm will provide 90% power. The expected average annual recruitment is 5-10 patients / site. We will aim to roll out the trial in 29 adult trauma-receiving hospitals in the UK. According to the timeline presented below, the recruitment will be completed in 3 years.

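### MAST-DURATION schedules its last AESI assessment at 6 months, although the outcome is AESIs during treatment and treatment may continue to 24 months

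*Protocol*

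**What the plan says.** Protocol 8.6.2 lists "Adverse events of special interest during treatment" as a secondary outcome of both trials. Section 11.5.2 repeats it as an assessment, "Adverse events of special interest review during treatment", and neither place sets an end date other than the end of treatment.

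On exposure, 10.1.1.4 (repeated for phenytoin in 10.1.2.4) states: "Participants will receive a maximum of up to 3 months or a minimum of 6 months as determined by the randomisation". It adds: "The maximum possible duration of treatment during the trial is 24 months dependent on clinical need".

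In the MAST-DURATION table of 11.6, "Treatment duration>6mths" is marked at all seven visits. "AESI assessment" is marked at baseline, discharge and 6 months, and not at 12, 18 or 24 months. A detached note to that table reads "If clinical indicated"; the extracted text does not show which marks it qualifies.

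The items that 11.5.2 lists for the 6- to 24-month contacts are seizures, GOSE, NSI, EQ-5D-5L and the Liverpool Adverse Events Profile. AESIs are not among them. Sections 11.5.2 and 11.7 have these contacts made remotely, in writing or by call.

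Two provisions are not tied to visits. Section 12.1.1 requires listed AESIs to go on the AESI form in both trials, and 12.5 makes each Principal Investigator responsible for recording all of them.

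**The concern.** The outcome is defined by time on treatment, but scheduled ascertainment ends at a fixed visit. That visit falls at the earliest point at which longer-arm treatment is allowed to end. Any treatment beyond it belongs to the outcome period and has no scheduled AESI question.

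This matters because side effects are the protocol's own counterweight to benefit. Section 16.3 says: "In view of the potential for increase in side effects with a longer course, we will aim for a relatively large treatment effect of 13" (percentage points). A reader weighing that benefit against harm will look to the AESI comparison. If ascertainment weakens at month 6, the comparison describes the first six months of the longer course better than the rest, and the shorter arm's allocated course is already over by then.

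**Working it through.** **The plan's own figures.** The protocol states no figure for AESI coverage. The nearby figures in 16.3 reproduce: 25% − 12% = 13 points, 1/0.13 = 7.7, and 428 × 0.88 / 2 = 188.3, which is the stated 188 per arm. Power with 188 per arm is 0.904 against the stated 90%. None of these depends on the present point.

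**Inputs.**
- L, month of the last scheduled AESI assessment: 6 (11.6).
- Visit window: ± 8 weeks (11.5.1), or 56/30.4375 = 1.84 months, so L may be 4.16 to 7.84.
- D, months on treatment: up to 3 in the shorter arm; at least 6 and at most 24 in the longer arm (10.1.1.4).
- Assumption: treatment time and contact time are counted from the same origin.

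**Formula.** Share of treatment time after the last scheduled AESI assessment = max(0, D − L) / D.

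| D (months) | L = 4.16 (early) | L = 6 (on time) | L = 7.84 (late) |
|---|---|---|---|
| 6 | 31% | 0% | 0% |
| 9 | 54% | 33% | 13% |
| 12 | 65% | 50% | 35% |
| 18 | 77% | 67% | 56% |
| 24 | 83% | 75% | 67% |

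With an on-time contact, for example, (12 − 6)/12 = 50% and (24 − 6)/24 = 75%.

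**Shorter arm.** With D at most 3, max(0, 3 − 6)/3 = 0%. This holds even for an early contact, since 3 is below 4.16. The exception is a patient whose treatment continues after a seizure, which 9.3 allows in either arm.

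**Sister trial.** In the MAST-PROPHYLAXIS table, AESIs are marked at Day 1 and Day 7, which spans the whole 7-day course. There the schedule matches the outcome; in MAST-DURATION it does not.

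**With the later contacts added.** L becomes 24, and max(0, D − 24)/D = 0% for every D up to 24. If the last contact is 8 weeks early, a 24-month course has 1.84/24 = 8% uncovered.

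The average uncovered share, and the number of AESIs affected, would need the distribution of durations and the AESI rate over time. The protocol gives neither.

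**The case against.** The strongest reply is that AESIs after month 6 are still recordable. Sections 12.1.1 and 12.5 set no time limit, and 11.5.2 asks for review throughout treatment. A reader might take the closing sentence of the introductory text of section 12 as shutting that route, but it only relieves sites of reporting non-serious events to the central team. It does not cancel the duty to record AESIs. So one may not infer that AESIs after month 6 go uncollected. What is missing is a scheduled prompt, at a stage when contact is mostly remote and clinic review happens only if the patient attends routinely (11.7).

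A second reply is that 24 months is a ceiling. The allocation is a 6-month minimum, continuation depends on clinical need, and the note "If clinical indicated" may qualify the later treatment marks. This stands: 75% is an upper bound, not a typical value.

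Third, harm after month 6 is measured in other ways: the Liverpool profile at 6, 12, 18 and 24 months, SAEs on the CRF, and mortality. This also stands in part. However, the Liverpool profile is a separate outcome, the protocol does not say that it captures the AESI list, and non-serious AESIs are not SAEs.

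Fourth, the gap is not confined to one arm. Section 9.3 lets treatment continue after a seizure whatever the allocation, and 16.3 assumes late seizures in 25% of the shorter arm against 12% of the longer. Claims that the loss falls only on the longer arm, or always favours it, therefore fail.

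Lighter scheduled AESI capture can be defended in a risk-adapted pragmatic trial, but the outcome should then be worded to match.

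**Conclusion.** The point holds as a mismatch between a named secondary outcome and its assessment schedule. Scheduled AESI assessment in MAST-DURATION ends at 6 months, while the outcome runs as long as treatment does. With an on-time contact, the share of treatment time without scheduled assessment is 0% at 6 months, 50% at 12 and at most 75% at 24. The 8-week window moves that last figure between 67% and 83%.

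Because only the longer arm is allocated treatment past 3 months, the gap falls mainly there, and under-ascertainment of AESIs with longer treatment is likely. That direction rests on two assumptions: that unprompted recording finds fewer events than a scheduled question, and that treatment past month 6 is more common in the longer arm.

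A reader might go further and conclude that the trial as a whole understates the harm of longer treatment by a known amount. The protocol does not support this, because other harm measures continue to 24 months and neither treatment durations nor AESI rates are given. The primary endpoint and the sample size are unaffected. Nothing here bears on how long patients should be treated.

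**What to change.** Reconcile 8.6.2, 10.1.1.4 (with 10.1.2.4), 11.5.2, 11.6 and 12.5 in one of two ways.

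1. Preferred: add a short AESI checklist, covering the time since the last contact, to the existing 12-, 18- and 24-month contacts for every participant in both arms. Mark it in 11.6 and list it in 11.5.2. Report AESIs by randomised arm. If a rate per treatment-month is also reported, count only treatment time up to each patient's last completed AESI assessment.
2. Otherwise: restate the MAST-DURATION outcome as AESIs up to 6 months, and do not describe it as covering treatment.

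The first option needs no new visits or patients. It makes three contacts slightly longer, and AESIs collected remotely are self-reported, so laboratory or clinical diagnoses on the list, such as macrocytosis or hepatitis, will be captured less reliably. The second option costs only a wording change, but leaves treatment after month 6 outside the AESI comparison.

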#### MAST-DURATION

If clinical indicated

# 11.7 Long-Term Follow-up Assessments

Participants will be followed up for 24 months post randomisation by postal questionnaire. However, if after approximately 2 weeks the questionnaire has not been returned then patients will be followed up by telephone. If the time point after an assessment exceeds 8 weeks, and there is no response, then the patient will be deemed as lost to that follow up. Where patients attend for a routine clinical follow-up they will be reviewed.

## 11.8 End of Trial Participation

Participants will continue normal standard of care following their participation in the trial.

## 11.9 Trial restrictions

There are no trial related restrictions in addition to standard care.

The management of any post-traumatic seizures will be based on the clinical assessment of the participant. Regardless of the trial arm the participant is assigned to, and the trial medications being/not being taken, the treating clinician will assess the participant regularly and will decide whether additional treatment is indicated. This may include additional anti-epileptic medication.

Trial medicines could reduce the effectiveness of oral contraceptives. It is therefore necessary to advise all participants, to take extra precautions while taking the trial medication and consider using alternative forms of contraception. If it becomes evident that a child between 10 and 16 years is sexually active, then safeguarding concerns will be discussed with the local site's named or designated safeguarding professional. Contraceptive advice is a particularly sensitive issue for young people and the Child PIS advises that their doctor will be able to discuss alternative types of contraception with them confidentially. Paediatric Certified Nurse Practitioners will be able to discuss this with them if they prefer. They will also be advised that their parents/legal guardians can provide more details on which types of contraception are suitable for them in this study.

Contraception advice will be as clinically directed. Due to the risks associated with Phenytoin, women of childbearing potential who are taking this IMP, who are in MAST-DURATION, will be advised not to become pregnant during treatment, or within one month of stopping IMP.

# 12 Assessment of Safety

Phenytoin is licensed for the treatment of epileptic seizures and for the prevention and treatment of PTS. Levetiracetam is licensed as monotherapy for the treatment of epileptic seizures in adults >16 years old, and as an adjunct treatment from 1 month of age. Levetiracetam is not licensed for either the treatment or prevention of PTS. It is, however, widely used off-license in both indications, in both adults and children. In a survey conducted at all UK neurosurgical units it was found that levetiracetam is more frequently prescribed than phenytoin for seizure prophylaxis .

The safety profiles of both drugs are well established and the trial participants will be assessed at regular intervals throughout the trial, over and above routine clinical care. Given the pragmatic nature of the trial, and that the potential risk associated with the study drug is 'no higher than standard care', the MAST trial will utilize the following risk-adapted safety reporting approach:

SAEs will be recorded in the CRF but not reported to the sponsor unless they are deemed to be SARs or SUSARs.

- Reactions that are either serious (SARs) or serious and unexpected (SUSARs) will require expedited reporting. Principal Investigators will be required to record and report SARs and SUSARs to the Sponsor as described in section 12.5
- All SAEs will be captured on the CRF for review by the CI (or delegated member of the coordination team).
- The resulting report listing of SAEs will be reviewed by the CI and reported to the Sponsor every 6 months.
- Reports of SAEs and reported SARs & SUSARs will form the basis of the Development Safety Update Report (DSUR) to be submitted annually to the MHRA and REC.

Principal investigators are not required to report to the central coordinating team any AEs or ARs unless these fulfill the criteria for a SAR or SUSAR.

# 12.1 Definitions

## 12.1.1 Adverse event (AE)

Any untoward medical occurrence in a participant or clinical trial participant administered a medicinal product and which does not necessarily have a causal relationship with this treatment.

An adverse event can therefore be any unfavourable and unintended sign (including an abnormal laboratory finding), symptom, or disease temporally associated with the use of an investigational medicinal product, whether or not considered related to the investigational medicinal product.

Please note: Recording of adverse events must start from the point of Informed Consent regardless of whether a participant has yet received a medicinal product.

However due to the pathology of traumatic brain injury, where the patients will be regularly monitored in the intensive care environment or on the neurosurgical wards, it is not practicable to record all adverse events. Therefore only adverse events of special interest (AESIs) will be recorded and **reportable** serious adverse events (SAEs) will be reported in accordance with this protocol. (Please see Section 12.1.4 for details of SAEs that are exempt from expedited reporting.)

#### Adverse events of special interest (AESI)

The following should all be recorded on the AESI form in the CRF for both trials:

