#### Secondary

- Compare outcomes between the three arms
  - extended Glasgow Outcome Scale
  - cognitive function
  - quality of life (EQ-5D-5L)
  - Liverpool Adverse Events Profile
- To compare adverse events between the three arms
- To compare the frequency of PTS between the three arms
- Compare the PTS rate between phenytoin and levetiracetam
- Undertake a detailed economic evaluation.

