# 9.3 Treatment Assignment

## MAST-PROPHYLAXIS

Patients who fulfil the eligibility criteria will be randomly assigned to either phenytoin, levetiracetam or no AED for a period of 7 days. The distribution between trial populations will be 1:1:1 (phenytoin : levetiracetam : no AED).

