#### Phenytoin arm

- Cardiovascular: Cardiac arrhythmia, circulatory shock;
- Central nervous system: phenytoin toxicity (nystagmus +/- unsteady gait +/- slurred speech +/- confusion). Drowsiness, suicidal ideation/tendencies;
- Dermatologic: Bullous dermatitis, skin rash;
- Gastrointestinal: Gingival hyperplasia;
- Genitourinary: Peyronie's disease;
- Hematologic: Macrocytosis, megaloblastic anaemia;
- Hepatic: Dupuytren's contracture, hepatitis ;
- Injection site reaction: Purple glove syndrome: oedema, discolouration and pain distal to injection site.

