#### Levetiracetam arm

• Central nervous system: Behavioural problems including: aggression, agitation, anger, anxiety, apathy, depersonalisation, emotional lability, irritability, neurosis, psychotic symptoms, suicidal ideation/tendencies.

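### MAST-PROPHYLAXIS lists its adverse events of special interest by drug arm, with no list for the no-AED arm, so the wording allows acute harms to be sought differently in the arms being compared

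*Protocol*

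**What the plan says.** **Lists.** Section 12.1.1 says that, because of the nature of the injury, not all adverse events can be recorded; AESIs are recorded, along with serious events. The AESI lead-in reads "The following should all be recorded on the AESI form in the CRF for both trials". Two lists follow. The one headed "Phenytoin arm" covers cardiovascular, nervous-system, skin, gingival, genitourinary, haematological, hepatic and injection-site items. The one headed "Levetiracetam arm" has only behavioural items, beginning "Behavioural problems including: aggression, agitation, anger, anxiety, apathy, depersonalisation". There is no third list.

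**Arms.** For MAST-PROPHYLAXIS section 9.3 states: "The distribution between trial populations will be 1:1:1 (phenytoin : levetiracetam : no AED". In MAST-DURATION the randomised arms are durations (up to 3 months or at least 6 months), and the drug is chosen locally.

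**Comparison and window.** Section 8.5.1 has the secondary objective "To compare adverse events between the three arms", listed separately from the Liverpool Adverse Events Profile. Section 8.5.2 has the two-arm equivalent. The outcome in section 8.6.2 is "Adverse events of special interest during treatment", and section 11.5.2 sets the same limit on the AESI review. For MAST-DURATION section 10.1.1.4 adds: "The maximum possible duration of treatment during the trial is 24 months dependent on clinical need".

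**Schedule (section 11.6).** AESI assessment falls at Day 1 and Day 7 in MAST-PROPHYLAXIS, and at baseline, discharge and 6 months in MAST-DURATION. Neither row is split by arm.

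**The concern.** A between-arm comparison of harms needs the same events sought in the same way over the same period in every arm. In MAST-PROPHYLAXIS the headings point the other way. Taken at face value, rash is sought on phenytoin only, agitation on levetiracetam only, and controls are asked about neither. The trial is open label (section 8.1), so staff know which heading applies.

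Several listed items, such as agitation, confusion and drowsiness, could plausibly arise from the brain injury itself. The no-AED arm is what would separate drug effect from injury, and it is the arm without a list. The protocol's own text shows a further gap: section 6.1 names drowsiness as a side effect of levetiracetam, but section 12.1.1 lists it only under phenytoin. The comparison between the two drugs is therefore exposed as well.

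Events that were never recorded cannot be recovered by any later analysis plan.

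**Working it through.** The protocol states no AESI rate or safety power, so there is no figure to reproduce. The check compares the text first and then sizes the possible bias.

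**1. Do the lists differ by randomised arm?**
- MAST-PROPHYLAXIS: three arms, two lists, one shared item (suicidal ideation/tendencies). If the headings are followed, ascertainment differs by arm.
- MAST-DURATION: both drugs can occur in both arms, and there is no untreated arm. A drug-specific list applies alike to both arms and creates no between-arm bias. The headings simply correspond to no randomised arm. Section 9.4 allows a switch to the other trial drug, after which the applicable list is undefined.

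**2. Can other data replace the acute comparison in MAST-PROPHYLAXIS?**
- The Liverpool profile is first collected at 6 months (sections 8.6.2 and 11.6), long after the 7-day course.
- Serious events are captured in all arms (section 12) but do not cover non-serious harm.
- The Day 1 and Day 7 visits fix when AESIs are assessed, not which items are asked of whom.

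The AESI form is therefore the only structured source for acute non-serious events.

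**3. Size if the headings are followed (MAST-PROPHYLAXIS).** Take n = 358 per arm (section 16.3; 1221 × 0.88 / 3 = 358.2). Assume true rate r in two arms, with the event recorded in only one, so the recorded rates are r and 0. For an unadjusted two-sided 5% test:

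probability = Φ{[r − 1.96·√(2·p̄(1−p̄)/n)] / √(r(1−r)/n)}, with p̄ = r/2.

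For r = 0.02: √(2 × 0.01 × 0.99/358) = 0.00744 and √(0.02 × 0.98/358) = 0.00740. Then (0.02 − 1.96 × 0.00744)/0.00740 = 0.73, and Φ = 0.77.

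| Assumed true rate | Expected recorded events | Chance of false significance |
|---|---|---|
| 1% | 3.6 v 0 | 48% |
| 2% | 7.2 v 0 | 77% |
| 5% | 17.9 v 0 | 99% |
| 10% | 35.8 v 0 | about 100% |

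The normal approximation is poor in the first row. Fisher's exact test needs at least 6 v 0 (p = 0.031; 5 v 0 gives 0.062). The binomial probability of 6 or more events in 358 is 15% at r = 1%, 72% at 2% and over 99% at 5%. The message is unchanged from about 2% upwards. If every arm uses the same list, this bias is zero at any rate.

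**4. The window.** In MAST-PROPHYLAXIS the no-AED arm has no treatment period, although the schedule already gives Day 1 and Day 7 to every arm. In MAST-DURATION a treatment-period window means up to 3 months against at least 6, possibly 24. The schedule instead assesses both arms at baseline, discharge and 6 months. The two disagree in both directions: short-course participants are assessed after treatment should have ended, and long-course treatment may continue after the last assessment.

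This matters only if the treatment-period wording overrides the schedule. In that case, take 188 per arm (section 16.3; 428 × 0.88 / 2 = 188.3) and an assumed equal hazard of 1% per month. The cumulative rates are 1 − exp(−0.03) = 3.0% and 1 − exp(−0.06) = 5.8%. Window length alone then gives a significant difference 27% of the time (16% to 83% for hazards of 0.5% to 5% per month). If the schedule governs, this does not arise.

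**The case against.** The strongest reply is that the lead-in says the items should all be recorded, on one form serving both trials. MAST-DURATION has no drug arms, so the headings cannot be randomised arms throughout. They may only label which drug each item relates to. The schedule does not split AESI assessment by arm, and section 12.1.1 starts recording at consent whether or not drug has been given. On that reading there is no bias. The form itself is not available to settle it. This stands as far as it goes: the fault is an ambiguity. But nothing in the protocol says that every item is checked in every arm, the headings say arm, and sites could reasonably follow them.

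A second reply is that the synopsis ties the adverse-event comparison to the Liverpool profile, which uses the same questionnaire at the same times in every arm, and that serious events are captured without regard to arm. This defeats any claim that adverse-event comparisons as a whole are compromised. It does not meet the acute gap, because section 8.5.1 lists the adverse-event comparison separately from the Liverpool profile, which starts at 6 months.

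A reader might infer that the safety comparison is invalid in both trials, or that MAST-DURATION has a built-in 2:1 excess from 6 against 3 months of observation. The documents support neither. Drug-specific lists fall equally on the two duration arms, and the schedule assesses both arms at 6 months. Handling of unequal exposure may also be set out in the statistical analysis plan, which is not shown.

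**Conclusion.** The concern holds as a wording fault that puts the AESI comparison in MAST-PROPHYLAXIS at risk. Whether bias occurs depends on how sites read section 12.1.1. If they follow the headings, a false difference is likely for any event with a true rate of roughly 2% or more; if they use one list, there is none. The rates are assumptions, as is complete non-recording in the unlisted arm. Partial recording would give a smaller bias.

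In MAST-DURATION the finding is narrower: headings that fit no randomised arm, and an outcome window that contradicts the schedule and needs reconciling. That months 6 to 24 have no AESI visit is not by itself a defect to be fixed here. The Liverpool profile continues at 12, 18 and 24 months in both arms, and extending AESI capture would be a debatable enlargement of the design.

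Primary endpoints and power are unaffected. The correction should still be prompt, because acute events missed in participants already enrolled may be unrecoverable.

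**What to change.** - In section 12.1.1, state that one combined AESI list is recorded for every participant in every arm of both trials, including no AED. Remove the arm headings, or relabel them as the drug with which each item is associated.
- In sections 8.6.2 and 11.5.2 and the synopsis, replace the treatment-period limit with a common window from randomisation: Day 1 to Day 7 in all three MAST-PROPHYLAXIS arms, and the scheduled assessments up to 6 months in both MAST-DURATION arms, whether or not the participant is still on drug.
- Check that the AESI form and site instructions match.

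The cost is protocol and CRF wording and slightly more form completion, mainly in the no-AED arm. No new visits are needed.
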